12.2 Analysis Endpoints

Primary Endpoint:

- ORR: The percentage of patients who achieve a best response of CR or PR, confirmed according to RECIST 1.1. Best response is recorded between the date of first dose and the date of documented progression per RECIST 1.1 or the date of subsequent anti-cancer treatment, whichever occurs first. For patients without documented progression or subsequent anti-cancer treatment, all available tumor assessments will contribute to the best response assessment.

Secondary Endpoints:

- CBR: The percentage of patients who achieve best response of confirmed CR or PR, or stable disease (SD) for at least 12 weeks. Best response is assessed as described for ORR.
- DOR: The interval from which measurement criteria are first met for CR or PR until the first date that progressive disease is objectively documented or death, whichever occurs first. Patients who have not progressed or died will be censored on the date of last evaluable tumor assessment; patients who did not have any on-study assessments and have not died will be censored on the date of first dose. If a patient receives subsequent anti-cancer treatment before documented progression, then DOR will be censored on the last evaluable tumor assessment on or before the start date of subsequent anti-cancer treatment.
- PFS: The time from start of CDX-3379 to time of progression or death, whichever occurs first. Patients who have not progressed or died will be censored on the date of last evaluable tumor assessment; patients who did not have any on-study assessments and did not die will be censored on the date of first dose. If a patient receives subsequent anti-cancer treatment before documented progression, then PFS will be censored on the last evaluable tumor assessment on or before the start date of subsequent anti-cancer treatment.
- OS: The time from start of CDX-3379 to death. Patients who have not died will be censored on the date of last contact.
- Safety: Safety will be assessed by vital sign measurements, clinical laboratory tests, physical exams, ECGs, and the incidence and severity of adverse events (graded according to NCI CTCAE v 5.0).
- Pharmacokinetics: Noncompartmental PK parameters will be determined using CDX-3379 serum concentration data obtained prior to, at completion of, and one hour after each CDX-3379 administration as well as on days 8 and 15 of the first cycle; and 30 days post-treatment.
- Immunogenicity: Patients will be monitored for the development of ADA to CDX-3379. Samples will be collected for future evaluation of the neutralizing capacity of ADA.
- Biomarkers: DNA sequencing will be conducted on tumor samples to assess for mutations in cancer-related genes such as FAT1, NOTCH1, NOTCH2, NOTCH3, AKT/PI3K, phosphatase and tensin homolog (PTEN) or ErbB family members.

[REDACTED]

[REDACTED]

[REDACTED]

12.3 Interim Analysis

No formal interim analysis is planned for this study. The sponsor may periodically conduct descriptive analyses while the study is ongoing. Because no formal hypothesis testing is planned, these periodic reviews will not require the overall type 1 error to be adjusted.

12.4 Analysis Populations

All treated population: All patients treated with CDX-3379. The primary efficacy analysis as well as all safety, PK, and biomarker analyses will be performed in this population. Efficacy analyses will also be conducted in the following subgroups: FAT1 mutation-positive treated patients, FAT1 or NOTCH mutation-positive treated patients, and all treated patients with a primary tumor site of oral cavity.

Response-evaluable population: All patients who have measurable disease at baseline and receive one full dose of both CDX-3379 and cetuximab and have post baseline tumor response assessment or discontinue study prematurely for disease progression, symptomatic deterioration, or death. Patients who discontinue treatment prior to the first tumor assessment for other reasons will be excluded from this population. Sensitivity analyses for efficacy endpoints will be performed in this population.

12.5 Statistical Methods

The primary study analysis is planned upon achievement of complete data for ORR assessment (i.e., after all treated patients have either experienced a tumor response or discontinued study treatment, or 6 months after the last patient has received their first dose, whichever occurs sooner).

Following primary analysis, study follow-up will continue until adequate data are available to support secondary analyses (see Section 7.5). Final analysis will be performed upon completion of the study, after the resulting clinical database has been cleaned, quality checked, and frozen.

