16. To be collected at 30-day follow-up visit, only if additional anticancer therapy has not been started.
17. Biomarker blood samples to be collected predose at Cycle 2, 3, 5, 7, and 9.

Continued (page 2 of 3)

Exhibit 4. Schedule of assessments, continued

	Screening	Treatment Period				End of Treatment (EOT) ²	Follow-up Period ³		
		Cycle 1		Cycle 2 and subsequent cycles					
		Day 1	Day 8	Day 15	Day 1		30-day	Survival follow-up	
Visit Window ¹	Day -28 to -1		± 1 day	± 1 day			± 3 days	Every 12 weeks ± 2 weeks until study closure	
Diagnostic imaging/ response assessment ¹⁸	×				× ¹⁸	× ¹⁸		× ¹⁸	
Administer CDX-3379 ¹⁹		×			×				
Administer cetuximab ²⁰		×	×	×	×				
Concomitant medication review ²¹	×	×	×	×	×	×	×	×	
Adverse event monitoring ²²		×	×	×	×	×	×	×	
Survival follow-up								×	
18. Disease evaluation done at screening, near the end of every 2nd cycle (i.e., after day 15 of Cycles 2, 4, 6, 8, etc. and prior to dosing for the next cycle), and, for patients who have not experienced progression at end of treatment, every 12 (±2) weeks until progression or initiation of alternate cancer therapies. Disease evaluation is required at end of treatment only if disease progression is not previously documented. If a partial or complete response is noted, a follow-up radiographic assessment must be done no sooner than 28 days later to confirm response. Prior to any intervention (such as surgical resection, palliative radiation or alternate anticancer therapy), every effort should be made to perform a tumor response assessment in order to document progression and/or confirm an objective response.									
19. Unless otherwise specified, all study assessments should be performed prior to administration of study treatment and may be performed up to 24 hours prior to treatment administration if assessments remain within the specified visit window. CDX-3379 should be administered first, with a 1-hour observation period before administration of cetuximab.									
20. Cetuximab will be administered weekly on Days 1, 8, and 15 of each cycle. On Day 1 of each Cycle, cetuximab should be administered approximately 1 hour after the completion of CDX-3379 administration and after collection of the 60 minute post-infusion PK blood sample. As a routine precaution, patients should be observed for at least 1 hour after the end of the cetuximab infusion.									

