5.6. Prior anti-cancer therapies

The number and percentage of patients who underwent prior cancer-related surgery, radiation, and systemic therapies will be summarized. Prior systemic therapy regimens will be categorized and presented by WHO Drug Preferred Name and summarized as:

- The number and percentage of prior systemic cancer therapy regimens (1, 2, 3, 4, 5 or more),
- The number and percentage of prior systemic cancer therapy regimens in the advanced/metastatic setting, and
- Types of prior systemic cancer therapies of interest, as categorized by medical review.

The best response (CR, PR, stable disease [SD], progressive disease [PD], or unknown) to the most recent prior regimen will be presented in addition to the reason for discontinuing.

6. Efficacy analyses

To support calculation of ORR, CBR, DOR, and PFS, tumor assessments will be performed approximately every six weeks during treatment. Patients who discontinue treatment in the absence of progression will continue to have assessments approximately every 12 weeks until documented progression or initiation of alternate anti-cancer therapies. The investigator will assess tumor response in accordance with RECIST 1.1 guidelines [2] (see Section 10.3). The investigator will record the overall response at each timepoint (CR, PR, SD, PD, or NE) as well as the date of first response (CR or PR) and date of PD. Best overall response (BOR) will be derived from timepoint responses per RECIST 1.1 guidelines.

The efficacy analyses will be conducted within the estimand framework. The details are provided in Appendix 10.1.

The primary analysis is planned upon achievement of complete data for ORR, i.e., after all treated patients have been followed for at least six months after receiving their first dose of study treatment or after all patients have discontinued study treatment, whichever occurs sooner.

Following the primary analysis, study follow-up will continue until adequate data are available to support secondary analyses.

The primary efficacy analysis will be based on the all treated population. Additional supportive efficacy analyses will be performed using the FAT1 mutation-positive treated patients, FAT1 or NOTCH mutation-positive treated patients, and all treated patients with a primary tumor site of oral cavity. A patient is considered NOTCH mutation-positive if they express a mutation in any one of the NOTCH family genes (NOTCH1, NOTCH2, or NOTCH3).

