6.1. Primary efficacy endpoint

The primary efficacy endpoint of this study is ORR, defined as the percentage of patients who achieve a best response of CR or PR, confirmed according to RECIST 1.1. That is, the criteria for response (CR or PR) must be met again at the next scheduled tumor assessment no sooner than 28 days after the initial documentation. Best response is recorded between the date of first dose and the date of documented progression per RECIST 1.1 or the date of subsequent anti-cancer treatment, whichever occurs first. Anti-cancer treatment includes (a) systemic anti-cancer therapy or (b) radiation or surgical resection of a target or non-target lesion. All anti-cancer treatments will be reviewed and confirmed by the Celldex medical team. For patients without documented progression or subsequent anti-cancer treatment, all available tumor assessments will contribute to the best response assessment.

The number and percentage of patients in each category of BOR (CR, PR, SD, PD, or not evaluable [NE]) will be summarized for the all treated population. ORR will be calculated as defined above, and the corresponding two-sided 95% exact CI will be calculated using the Clopper-Pearson method.

A waterfall plot showing the maximum change from the baseline sum of the diameters of target lesions will be produced for the response-evaluable population. Subgroup waterfall plots may be produced.

A swimmer plot will be produced to present individual patient's tumor response and duration of response over time.

A spider plot will be produced to present change in an individual patient's tumor size with tumor size relative to baseline plotted against month from baseline scan; new lesion and end of treatment dates will be annotated in the plot. Subgroup spider plots may be produced.

Change from baseline in tumor size will be calculated as: Sum of diameters at Week X (mm) – Sum of diameters at Baseline (mm). Percent change from baseline in tumor size will be calculated as: (Sum of diameters at Week X (mm) – Sum of diameters at Baseline (mm)) / Sum of diameters at Baseline (mm) * 100%.

All primary and secondary efficacy outcomes (BOR, DOR if applicable, date of PD if applicable, PFS status, and OS status) will be presented in a single by-patient listing. Individual timepoint assessment data for each lesion will be presented in a separate listing.

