10.1. Estimand framework

A summary of the attributes of the primary estimand is provided in Table 1.

Table 1. Estimand attributes for the primary efficacy analysis

Estimand attribute	Description of attribute
Target population	All treated population: All patients treated with CDX-3379.
Primary patient-level variable	Best overall response (BOR) according to RECIST 1.1. Patients can have a BOR of complete response (CR), partial response (PR), stable disease (SD), progressive disease (PD), or unknown.
Handling of intercurrent events	Alternative anti-cancer therapies will be intercurrent events in the determination of BOR. Assessments that occur after the date of documented progression per RECIST 1.1. or the date of anti-cancer treatment, whichever occurs first, will not contribute to the determination of BOR.
Population-level summary	ORR, defined as the percentage of patients who achieve a best response of CR or PR, confirmed according to RECIST 1.1., for all patients treated with CDX-3379 in combination with cetuximab.

The trial product estimand is defined as ORR based on assessments on or prior to the date of PD or data of anti-cancer therapy, whichever occurs first. Patients who discontinue study therapy for reasons other than progression will continue to have tumor assessments until disease progression or initiation of subsequent anti-cancer therapy, whichever occurs first. Therefore, treatment discontinuation is not considered an intercurrent event. The primary efficacy analysis will be an estimation analysis for this estimand (point estimate of ORR and associated 95% confidence interval).

Duration of response is an important secondary analysis because it characterizes ORR. A summary of the attributes of the estimand associated with this important secondary endpoint is provided in Table 2.

Table 2. Estimand attributes for the important secondary efficacy analysis

Estimand attribute	Description of attribute
Target population	All patients treated with CDX-3379 who have a BOR of confirmed CR or PR (objective response).

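### The SAP's primary-analysis trigger can fire before a late first response has had its confirmatory scan, so the confirmed ORR can be slightly undercounted

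*Protocol*

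**What the plan says.** **Endpoint.** Protocol 12.2 defines ORR as "The percentage of patients who achieve a best response of CR or PR, confirmed according to RECIST 1.1". SAP 6.1 adds that the response criteria "must be met again at the next scheduled tumor assessment no sooner than 28 days after the initial documentation". Note 18 to the schedule of assessments (Protocol Table 1, SAP Exhibit 4) says that "a follow-up radiographic assessment must be done no sooner than 28 days later to confirm response".

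**SAP trigger (Section 6).** One limb is met "after all treated patients have been followed for at least six months after receiving their first dose of study treatment". The alternative limb, which decides the date if it comes first, is met "after all patients have discontinued study treatment, whichever occurs sooner". The SAP describes this as the point at which ORR data are complete.

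**Protocol trigger (12.5).** One limb is met "after all treated patients have either experienced a tumor response or discontinued study treatment". The alternative limb is a time limit: "6 months after the last patient has received their first dose, whichever occurs sooner". The protocol also calls the ORR data complete at that point.

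**Assessments after treatment stops.** Patients who stop without progression are scanned about every 12 (±2) weeks, and those scans count towards best response. SAP 10.1 concludes: "Therefore, treatment discontinuation is not considered an intercurrent event".

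**Which document governs.** SAP Section 1 says that its methods prevail where they differ from the protocol. Protocol Section 12 allows the SAP to modify the protocol's plans, and asks for an amendment only for major changes to the primary endpoint definition or its analysis.

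**The concern.** The endpoint needs two scans at least 28 days apart. The trigger counts follow-up time or treatment discontinuation and never asks whether a response already seen has been confirmed or can no longer be confirmed. Data called complete may therefore include responses still waiting for their second scan.

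The error has one direction. Under SAP Exhibit 12, a PR followed by a non-evaluable time point becomes SD if the 12-week minimum is met and NE otherwise. The exhibit has no row for a second scan that is not yet due, so this is the nearest one. SAP 6.4 imputes nothing. A pending confirmation can remove a responder from the primary ORR and can never add one. With 45 patients, one responder can move the exact lower limit across a threshold that the sample-size section uses.

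**Working it through.** **1. The plan's own figure.** Protocol Table 11 gives 15/45 a 95% Clopper-Pearson interval of 20.0 to 49.0 and 86% power at a true ORR of 40%. Recomputed, the interval is 20.0 to 49.0 and P(X ≥ 15 | n = 45, p = 0.40) = 0.857. Both agree, so these figures are not at issue here.

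**2. Six-month limb (the same in effect in both documents).**
- Cut: SAP 4.4 sets 1 month = 30.4375 days, so 6 × 30.4375 = 182.6 days after the last patient's first dose.
- Scans: cycles last 21 days (SAP 2.3), with a scan after day 15 of every second cycle and before the next dose. The windows are about days 36-42, 78-84, 120-126 and 162-168.
- Earliest confirmation of a first response at week 24: 162 + 28 = 190 to 168 + 28 = 196.
- At the next scheduled scan, as SAP 6.1 words it: 162 + 42 = 204 to 168 + 42 = 210.
- All of these fall after day 182.6. In the last patient enrolled, the latest on-schedule first response that can be confirmed in time is at week 18, confirmed by day 168. The slack is 182.6 − 168 = 14.6 days, so a longer cumulative delay could lose that one too.
- For patients enrolled earlier, the exposed response is one first seen at the last scan before the cut.

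**3. All-discontinued limb (SAP).** If the last patient stops treatment with an unconfirmed response, the trigger is met at once, but the next routine scan may be about 12 weeks away. An end-of-treatment scan closes the gap only if it is at least 28 days after the first response.

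**4. Response limb (protocol only).** If the last outstanding event is a first response, the literal wording is met that day, at least 28 days short of confirmation. The SAP has no such limb.

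**5. Coding.** By week 24 the 12-week minimum for SD has passed, so the week-24 case becomes SD. NE arises only where that minimum is not met.

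**6. Effect of one lost response.** 1/45 = 2.2 points.

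| Count | ORR | Lower 95% limit |
|---|---|---|
| 15/45 | 33.3% | 20.0% |
| 14/45 | 31.1% | 18.2% |
| 12/45 | 26.7% | 14.6% |
| 11/45 | 24.4% | 12.9% |
| 5/15 (FAT1) | 33.3% | 11.8% |
| 4/15 (FAT1) | 26.7% | 7.8% |

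If one response were lost in every trial, the chance of reaching 15/45 at a true ORR of 40% would be P(X ≥ 16) = 0.775 instead of 0.857. That is a deliberately pessimistic case.

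**7. How often.** The documents do not give the timing of first responses, so this step rests on assumptions: even accrual of 45 patients, a true ORR of 10-40%, and 5-30% of first responses at week 24 or later. For each patient, multiply the ORR by the share of first responses falling at the last scan before the cut, then sum over patients. With the protocol's enrollment period of about 2 years, the expected number of unconfirmed responses is 0.01 to 0.28. With accrual in 1 year it is at most 0.55. Usually none is lost, occasionally one.

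**The case against.** A reader might infer that two triggers mean two possible primary ORRs, or that the data will be cut on the very day of an unconfirmed response. The documents do not support either reading. The SAP says that it prevails, and the protocol lets it modify the plan. The same-day cut exists only under the protocol's response limb, which the SAP dropped. Even there, the limb could decide the date only if every other patient had already responded or stopped, and its reference to a response can plausibly be read as confirmed, given the endpoint. What remains of this part is a mismatch in wording.

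Other points carry weight:

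- Neither trigger section fixes a data cut-off date, and the SAP sets six months as a minimum. A confirmatory scan obtained before database lock might be included in practice, although the plan does not say so.
- A final analysis is planned at study completion, estimated at about 1 year after recruitment ends (Protocol 7.5), and all available assessments count for patients without progression or new therapy. A late confirmation would probably be collected. But follow-up after the primary analysis is tied to secondary analyses, and neither document commits to updating ORR.
- Note 18 asks for every effort to confirm a response before another intervention, which reduces the loss.
- The analysis is estimation only, so 20% is a precision benchmark and not a success rule, and 15/45 against 14/45 is an example chosen at the boundary.
- Any fixed landmark misses first responses that occur after it.

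These points limit the size of the problem. They do not remove it, because the governing SAP is silent on confirmation in both of its limbs.

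**Conclusion.** The point holds as a minor defect in the timing rule. The SAP trigger can declare ORR data complete while a late first response still awaits its confirmatory scan, and the resulting error can only lower the primary ORR. The date arithmetic uses the documents' own figures and assumes scans on schedule. That 0 or 1 patient is affected rests on the assumed accrual pattern, ORR range and response timing. It also rests on the primary ORR being computed from data available when the trigger is met, which the documents imply but do not state.

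**What to change.** Use one trigger in both documents: 6 months after the last patient's first dose, or earlier if every patient has a confirmed response, progression, new anti-cancer therapy, death, withdrawal or loss to follow-up. Withdrawal and loss to follow-up need to be listed; otherwise one such patient would block the early limb.

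Add that, for any response first documented by the cut, the confirmatory assessment (at least 28 days later) is included before the primary ORR is finalised, unless confirmation is no longer possible. State also that ORR will be updated at the final analysis, which would pick up first responses after the cut.

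The cost is wording in Protocol 12.5 and SAP Section 6, with no change to the scan schedule. The primary analysis could be delayed by about 6 weeks for a patient on treatment, or by up to about 12-14 weeks if the patient stopped without progression and is on the 12 (±2)-week schedule.

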12.5.1 Efficacy Analyses

Best overall response (as defined by RECIST 1.1) will be summarized for the all treated population. ORR will be calculated as defined above, and the corresponding 95% exact CI will be calculated using the Clopper-Pearson method.

CBR will be analyzed using the same approach as ORR.

DOR will be estimated using the Kaplan-Meier (KM) product limit method. The KM estimate of the median DOR will be reported along with the two-sided 95% CI using Brookmeyer and Crowley's method (log-log transformation).

Progression-Free Survival and Overall Survival will be analyzed using the same approach as DOR.

Additional analyses may be conducted including estimating objective response rate and other efficacy parameters for the response-evaluable population and within biomarker defined subgroups.

12.5.2 Safety Analyses

Safety analyses will consist of data summaries for clinical and laboratory parameters, and for AEs. The number and percentage of patients experiencing one or more AEs will be summarized by the relationship to study drug and severity based on NCI CTCAE v 5.0. Adverse events will be coded using the Medical Dictionary for Regulatory Activities (MedDRA). Laboratory parameters will be summarized using descriptive statistics, by post-treatment shifts relative to baseline, and data listings of clinically significant abnormalities. Vital signs and ECG data will be summarized using descriptive statistics.

